4.1 Study Design Summary

Methodology:

Multicenter, randomized, double-blind, placebo-controlled, parallel-group, fixed-dose study

Number of Patients:

480 planned (approximately 160 per treatment group)

Diagnosis and Main Criteria for Inclusion:

Male and female outpatients who are 18 to 65 years of age, meet Diagnostic and Statistical Manual of Mental Disorders, Fifth Edition (DSM-5) criteria for bipolar I disorder without psychotic features confirmed by the administration of the Mini International Neuropsychiatric Interview (MINI), with a current major depressive episode of at least 4 weeks and not exceeding 12 months in duration, a minimum score of 20 on the 17-item Hamilton Depression Rating Scale (HAMD-17), a minimum score of 2 on item 1 of the HAMD-17, and a minimum score of 4 on the Clinical Global Impressions-Severity Scale (CGI-S) at Visits 1 and 2.

Test Product, Dosage, and Mode of Administration:

[figure not shown]
Cariprazine 1.5 mg/day and 3.0 mg/day capsules, oral administration

Duration of Treatment:

A no-drug screening period of approximately 7-14 days, followed by 6 weeks of double-blind treatment and a 1-week, no investigational product safety follow-up period.

Reference Therapy, Dosage, and Mode of Administration:

Matching placebo capsules, oral administration

4.2 Study Objectives and Endpoints

Each study objective is presented with corresponding endpoint(s) below:

Table 4-1 Study Objectives and Endpoints

Objectives	Endpoints

• To evaluate the efficacy of cariprazine 1.5 mg/day and 3.0 mg/day relative to placebo in patients with bipolar I depression	
Primary Efficacy Endpoint
 
• Change from baseline to Week 6 in Montgomery-Åsberg Depression Rating Scale (MADRS) total score 
Secondary Efficacy Endpoint
 
• Change from baseline to Week 6 in Clinical Global Impressions-Severity Scale (CGI-S)

[figure not shown]
[figure not shown]
Objectives	Endpoints
	
	
	

[figure not shown]
Table 4-2**Montgomery-Åsberg Depression Rating Scale (MADRS)**

Item List ^a	Score Range
1 Apparent sadness 2 Reported sadness 3 Inner tension 4 Reduced sleep 5 Reduced appetite 6 Concentration difficulties 7 Lassitude 8 Inability to feel 9 Pessimistic thoughts 10 Suicidal thoughts	(Each item is rated on a scale from 0 to 6.)

^a Scale for each item described in Appendix IV of the protocol.

Table 4-3**Clinical Global Impressions—Severity (CGI-S)**

Grade	Description
1	Normal, not at all ill
2	Borderline ill
3	Mildly ill
4	Moderately ill
5	Markedly ill
6	Severely ill
7	Among the most extremely ill patients

5. Statistical Methodology and Study Endpoints

5.1 Statistical Methods Planned in the Protocol and Determination of Sample Size

This statistical analysis plan (SAP) will be approved prior to database lock. The SAP expands the statistical section of the protocol and contains a detailed description of methods to analyze data collected in the study. The text portion of the SAP will be included in the CSR report as Appendix 16.1.9.

5.1.1 Statistical and Analytical Plans

Statistical analyses will be conducted using SAS Version 9.3 or newer.

5.1.1.1 Common Conventions

5.1.1.1.1 Analysis Populations

The analysis populations will consist of participants as defined below:

Table 5-1 Analysis Populations

Population	Definition	Study Treatment
Screened	All patients who signed informed consent and received a PID number	—
Randomized	All patients in the Screened Population who were randomized to a treatment group in the study.	Randomized assignment
Safety	All patients in the Randomized Population who took at least 1 dose of double-blind investigational product	Randomized assignment
Intent-to-Treat (ITT)	All patients in the Safety Population who had at least 1 postbaseline assessment of the MADRS total score.	Randomized assignment

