9.4.3 Method of Assigning Patients to Treatment Groups

Each study center will be provided with investigational products. An interactive voice/interactive Web response system (IxRS) will be used during the study to monitor enrollment and medication allocation. If the patient meets the randomization criteria, the study center will contact the IxRS at end of Visit 2 to randomize the patient. IxRS will randomize the patient to the appropriate treatment arm (placebo, cariprazine 1.5 mg/day, or cariprazine 3.0 mg/day) and determine the investigational product number to be assigned to the patient based on the randomization.

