Note: At Visit 2 and Visit 3 patients will be dispensed 1 blister pack. At Visit 4 and Visit 5, patients will be dispensed 2 blister packs. Each blister pack will contain 10 capsules, adequate for 7 days plus 3 extra days.

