9.7.1.3 Safety Population

The Safety Population will consist of all patients in the Randomized Population who took at least 1 dose of double-blind investigational product.

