5.1.1.1.3 Statistical Methodology

The methodologies defined below apply as specified to individual endpoints defined in this SAP. When indicated, 95% two-sided confidence intervals and two-sided p-values will be presented. Individual endpoint analyses may specify exceptions (additions or deletions) to these general definitions.

Table 5-2

Statistical Methodology

Methodology	Description
Categorical counts	
 Number of participants in individual categories 
 Participants with ≥ 1 qualifying event counted once per individual category
Categorical descriptives	
 Number and percentage of participants in individual categories 
 Participants with ≥ 1 qualifying event counted once per individual category $N1$ = number of patients with non-missing baseline For AE summary of sex-specific AEs, the percentage is based on the number of participants of the sex
PCS descriptives	
 Number and percentage of participants meeting potentially clinically significant (PCS) criteria 
 Participants with ≥ 1 qualifying event counted once per PCS category Percentage denominator = number of participants with non-missing baseline and ≥ 1 non-missing postbaseline assessment 
 Unevaluable assessments considered missing $N1$ = participants with non-missing values at both baseline and the specified postbaseline analysis visit
Shift analysis	
 Number and percentage of participants in individual baseline and postbaseline categories Percentage denominator = number of participants in individual baseline categories $N1$ = participants with non-missing values at both baseline and the specified postbaseline analysis visit
Continuous descriptives	
 N, mean, standard deviation (SD), median, minimum, maximum
CFB descriptives	
 Continuous descriptives for baseline, postbaseline, and change from baseline (CFB) values
	

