5.1.1.4 Safety Analyses

Safety analyses will be based on the Safety Population.

Baseline assessments for applicable safety endpoints defined as follows:

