5.1.1.4.2 Adverse Events

The following adverse event (AE) terms are defined:

Table 5-16 AE Terms

Term	Description
Treatment-emergent	An event that initially occurs or increases in severity on or after the treatment start date, where: 
 Treatment start date \leq event start date \leq treatment end date + 30
Newly-emergent	An AE occurring during the safety follow-up period will be considered a newly emergent adverse event if the AE was not present before the start of the safety follow-up period or was present before the start of the safety follow-up period and increased in severity during the safety follow-up period.
On-therapy	An event where: 
 Treatment start date \leq event start date \leq treatment end date + 30

AEs, encompassing abnormalities and surgeries reported as occurring after the Screening Visit, will be coded using MedDRA version 19.1 or newer. Unique patients reporting AEs in the following AE categories will be summarized by treatment group for the Safety Population as follows:

[figure not shown]
Table 5-17**AE Summaries**

Parameter	Description	Timing	Methodology
Overall summary	Overall summary only for the following categories: 
 • Deaths • Treatment-emergent AEs (TEAEs) • On-therapy Serious adverse events (SAEs) • AEs leading to discontinuation 	Double-blind Treatment Period	Categorical descriptives
	Overall summary only for the following categories: 
 • Deaths • Serious adverse events (SAEs) • Newly emergent AEs 	During the Safety Follow-up Period and within 30 days after the last dose of double-blind treatment	Categorical descriptives
TEAEs	Overall summary and by SOC and PT	Double-blind Treatment Period	Categorical descriptives
NEAEs	Overall summary and by SOC and PT	During the Safety Follow-up Period and within 30 days after double-blind treatment	Categorical descriptives
Common TEAEs	Summary by SOC, PT, sorted by decreasing frequency for the test treatment 
 • Includes TEAEs occurring in $\geq 2.0\%$ of participants in any treatment group. Event rates will not be rounded prior to comparison with the 2.0% cutpoint. Summary by PT, sorted by decreasing frequency for the test treatment	Double-blind Treatment Period	Categorical descriptives

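### SAP Table 5-1 classifies the Safety Population by randomized arm, and no as-treated rule is visible, so exposure and events on another arm's product would fall in the wrong column (minor, and only if mis-dispensing occurs)

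*SAP*

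**What the plan says.** SAP Section 5.1.1.1.1, Table 5-1, defines the Safety Population as "All patients in the Randomized Population who took at least 1 dose of double-blind investigational product". The decisive text is the Study Treatment column of that row, which reads "Randomized assignment". The Randomized and ITT rows carry the same entry.

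The safety tables inherit this. SAP Section 5.1.1.4 states: "Safety analyses will be based on the Safety Population". Section 5.1.1.4.2 adds: "Unique patients reporting AEs in the following AE categories will be summarized by treatment group for the Safety Population as follows". Exposure and compliance (Section 5.1.1.4.1) are likewise summarized by treatment group in that population.

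Protocol Section 9.7.1.3 has the same membership rule, "The Safety Population will consist of all patients in the Randomized Population who took at least 1 dose of double-blind investigational product", and does not say which treatment applies, so the SAP entry governs. SAP Section 5.1.1.1.3 leaves some room: "Individual endpoint analyses may specify exceptions (additions or deletions) to these general definitions". No readable section uses that room for treatment received.

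On supply, Protocol Section 9.4.3 has the IxRS randomize the patient and "determine the investigational product number to be assigned to the patient based on the randomization". Product is handed out at Visits 2, 3, 4 and 5. One pack is given at each of the first two, and then "At Visit 4 and Visit 5, patients will be dispensed 2 blister packs" (note to Table 9.4.5-1).

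**The concern.** A patient enters this population by taking product, yet which product was taken plays no part in the classification. If a placebo patient takes cariprazine in error, days on drug are credited to placebo in the exposure table, and a reaction to drug appears in the placebo column. If a cariprazine patient takes placebo, the drug column is diluted. For events commoner on drug, both errors shrink the drug-placebo difference. Analysis as randomized protects the efficacy comparison. In a safety table the same dilution is not conservative.

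The compliance summary would not reveal the error, because it counts capsules (Protocol Section 9.4.9; SAP Table 5-15) and the capsules look identical (Protocol Section 9.4.1).

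**Working it through.** **1. The plan's own figures.**
- SAEs in RGH-MD-56 (Protocol Section 7.0): placebo 5/145 = 3.4%; 1.5 mg and 3 mg 2/146 = 1.4% each. These reproduce.
- Power (SAP Section 5.1.2): 160 per arm, effect size 0.36, 22% dropout, correlations 0.6. The SAP's closed Simes procedure was simulated with its weights, assuming four visits, compound symmetry and a monotone dropout path (effective n 135 to 139 per arm). This gives 81% to 83% per dose, 90% to 91% for at least one dose, and 89% to 90% for the secondary given the primary. The plan states 82%, 90% and 88%.
- None of the power figures enters this point. Efficacy uses the ITT Population, which stays classified as randomized.

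**2. One patient with an event.** Take 160 per arm, the planned number; the dosed number may be slightly lower. The documents give no count of mis-dispensed patients, so the range is assumed:
- 1 patient: 1/160 = 0.63 points
- 2 patients: 2/160 = 1.25 points
- 5 patients: 5/160 = 3.1 points, if all five have the event

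**3. The common-TEAE cut-off.** SAP Table 5-17 lists terms reaching 2.0% in any arm, unrounded. 3/160 = 1.9% is not listed; 4/160 = 2.5% is. As an illustration, a term has 3 events on one dose, 1 on placebo and fewer than 4 on the other dose. The placebo event occurred in a patient who was taking that first dose.
- As randomized: 3/160 = 1.9% and 1/160 = 0.6%, so the term is not listed.
- As treated: 4/161 = 2.5% and 0/159 = 0%, so it is listed.

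**4. SAE counts.** The RGH-MD-56 arms matching this trial had 5, 2 and 2 SAE patients. One patient is 1/5 = 20% to 1/2 = 50% of such a count. That patient must also have an SAE, which happened in 1.4% to 3.4% of patients in those arms.

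**5. Expected dilution.** Suppose k placebo patients take active drug for the whole course. The expected placebo rate is [(160 − k) × p0 + k × p1]/160, a shift of k × (p1 − p0)/160.
- Assumed p0 = 2%, p1 = 10%, k = 5: 5 × 8/160 = 0.25 points.
- p0 = 55%, p1 = 62% (any TEAE in RGH-MD-56: placebo, and the top of the cariprazine range), k = 5: 5 × 7/160 = 0.22 points.

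**6. How long one error lasts.** The dispensing intervals are 1, 1, 2 and 2 weeks. For a completer, an error at one visit covers at most 2/6 = 33% of treatment. A swap between the two cariprazine arms on Days 1-14 changes nothing, because both take the same dose then (Protocol Section 9.4.5).

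**The case against.** The SAP's choice is explicit, prespecified and not in conflict with the protocol. IxRS product numbers exist to prevent mis-dispensing. Some of the ground is already covered. Departures in dosing are protocol deviations (Protocol Section 9.9). Important deviations are summarized by arm, and deviations are listed (SAP Table 5-6). Patients with SAEs or AEs leading to discontinuation are listed with all their AEs (SAP Table 5-17). All of this stands, and it keeps the point minor. It does not place an event under the product that was taken.

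A reader might infer more than the documents support:
- **That every laboratory, ECG and EPS table is affected.** Much of the SAP safety section is blacked out. No exception is visible, but one cannot be excluded.
- **That dilution always favours the drug.** This holds only for events commoner on drug. In RGH-MD-56, SAEs were commoner on placebo (3.4% against 1.4% on each matching dose). Dilution there would hide an advantage of the drug.
- **That one patient could double an SAE count.** That needs an arm with 1 SAE patient. In RGH-MD-56 this was the 0.75 mg arm, which this trial does not have.
- **That errors are likely because many packs are handed out.** Up to (1 + 1 + 2 + 2) × 480 = 2,880 packs are dispensed if everyone completes. Without an error rate, this counts opportunities and does not give a frequency.

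There is also a fair objection to a simple remedy that assigns each patient by the product taken for most of the period. It would leave a completer with a single-visit error in the randomized arm. If judged by capsule strength, it would also move 3.0 mg patients who stop before Day 28 to the 1.5 mg arm, because their first 14 days are at 1.5 mg by design. The fix has to avoid both.

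**Conclusion.** The point holds as a minor one. Table 5-1 states a rule that misattributes exposure and events whenever a patient takes another arm's product, and no readable section corrects it. If no such error occurs, nothing changes.

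If one does occur, an affected patient with an event moves an arm by 0.63 points. That is enough to decide the display of a term near the 2.0% cut-off, and it is 20% to 50% of an SAE count of the expected size. The average shift is much smaller: about a quarter of a point even with five placebo patients on active drug throughout, under the assumed rates. Efficacy, alpha and power do not depend on it.

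This rests on about 160 dosed patients per arm, on SAE counts like those of RGH-MD-56, and on the blacked-out text holding no as-treated rule.

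**What to change.** 1. In Table 5-1, change the Study Treatment entry of the Safety row to treatment actually received. Keep randomized assignment for the Randomized and ITT Populations.
2. Define treatment received by the arm's dispensed regimen, not by capsule strength. The planned 1.5 mg on Days 1-14 in the 3.0 mg arm then counts as 3.0 mg arm treatment, and patients who stop early are not moved. A patient changes arm only when packs from another arm's regimen were taken in error.
3. Fix the rule for mixed exposure before database lock. A rule chosen once codes and events are known would be post hoc.
4. List every patient whose received and randomized product differ, with the product being taken at the onset of each AE. This makes single-visit errors visible even when the patient stays in the randomized arm.

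If the sponsor prefers to keep randomized assignment, the minimum is a prespecified as-treated safety summary, to be produced if any discrepancy is found.

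**Cost:** one table cell, a short definition, one listing, and a small reconciliation of dispensed product numbers against the IxRS allocation. The documents describe product numbers on labels and in the IxRS, and site accountability records. They do not confirm that the dispensed number is in the analysis database, so that should be checked first.

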5.1.1.1.2 Study Treatments

The following treatment groups are defined for this study:

- Cariprazine 1.5 mg/day
- Cariprazine 3.0 mg/day
- Placebo

5.1.1.1.3 Statistical Methodology

The methodologies defined below apply as specified to individual endpoints defined in this SAP. When indicated, 95% two-sided confidence intervals and two-sided p-values will be presented. Individual endpoint analyses may specify exceptions (additions or deletions) to these general definitions.

Table 5-2

Statistical Methodology

Methodology	Description
Categorical counts	
 Number of participants in individual categories 
 Participants with ≥ 1 qualifying event counted once per individual category
Categorical descriptives	
 Number and percentage of participants in individual categories 
 Participants with ≥ 1 qualifying event counted once per individual category $N1$ = number of patients with non-missing baseline For AE summary of sex-specific AEs, the percentage is based on the number of participants of the sex
PCS descriptives	
 Number and percentage of participants meeting potentially clinically significant (PCS) criteria 
 Participants with ≥ 1 qualifying event counted once per PCS category Percentage denominator = number of participants with non-missing baseline and ≥ 1 non-missing postbaseline assessment 
 Unevaluable assessments considered missing $N1$ = participants with non-missing values at both baseline and the specified postbaseline analysis visit
Shift analysis	
 Number and percentage of participants in individual baseline and postbaseline categories Percentage denominator = number of participants in individual baseline categories $N1$ = participants with non-missing values at both baseline and the specified postbaseline analysis visit
Continuous descriptives	
 N, mean, standard deviation (SD), median, minimum, maximum
CFB descriptives	
 Continuous descriptives for baseline, postbaseline, and change from baseline (CFB) values
	

5.1.1.5 Site Pooling

For efficacy analyses in which study center is a factor, a small center will be defined as a center with fewer than 2 patients in at least 1 treatment group in the ITT Population. Small centers will be pooled to form pseudo-centers so that each treatment group includes at least 2 ITT patients within the center. Pooling will be done within each country using the following algorithm:

1. Based on the number of ITT patients, small centers will be ordered from the largest to the smallest, and centers of the same size will be ordered from the largest center number to the smallest center number.

2. The pooling process starts with the largest small center from the top, which will be pooled with the smallest from the bottom until a non-small center is formed.
3. The process will be repeated using the small centers left out after the first pass.
4. If any centers are left out at the end of the process, they will be pooled with the smallest pseudo-center. If there is more than 1 smallest pseudo-center, the pseudo-center with the smallest center number will be selected. In case that the pseudo center formed by pooling all small centers is still a small center, it will be pooled with the smallest non-small center. If there is more than 1 smallest non-small center, the one with the smallest center number will be selected.

The pseudo-centers will be used for all efficacy analyses when the model is adjusted for study center.

5.1.1.2 Demographics

5.1.1.2.1 Analysis Populations

The distribution of participants within the analysis populations will be summarized as follows:

Table 5-4 Analysis Population Summaries

Population	Description	Timing	Methodology
Screened Population	Distribution overall and within Study Center in total	—	Categorical counts
Randomized, Safety, and ITT Populations	Distribution overall and within Study Center in total and by treatment group	—	Categorical counts

5.1.1.2.2 Participant Disposition

Participant disposition encompasses the distribution of participants who enter, complete, and discontinue each specified analysis period, along with eCRF-reported discontinuation reasons from each respective analysis period. Participant disposition will be summarized as follows:

Table 5-5 Participant Disposition Summaries

Parameter	Description	Timing	Methodology
Screening disposition	Distribution in the Screened Population overall and within Study Center in total	Screening Period	Categorical descriptives
Double-blind disposition	Distribution in the Randomized, Safety and ITT Population overall and within Study Center in total and by treatment group	Double-blind Treatment Period	Categorical descriptives
Double-blind disposition	Distribution by reason in the Safety Population in total and by treatment group	Double-blind Treatment Period	Categorical descriptives

5.1.1.2.3 Protocol Deviations

Protocol deviations will be defined in Protocol Deviation Requirement Specification, including importance classification. Protocol deviations will be summarized as *follows for the Randomized Population:*

Table 5-6 Protocol Deviation Summary

Parameter	Description	Timing	Methodology
Important protocol deviations ¹	Distribution in the Randomized Population in total and by treatment group	—	Categorical descriptives

¹Protocol deviations will be listed.

5.1.1.2.4 Demographics

Demographics will be summarized in total and by treatment group for the ITT and Safety Populations, as follows:

Table 5-7 Demographic and Baseline Characteristics Summaries

Parameter	Description	Timing	Methodology
Age	Age (years) relative to informed consent date	Informed consent	Continuous descriptives
Age group	
 • < 20 years • ≥ 20 to < 30 years • ≥ 30 to < 40 years • ≥ 40 to < 50 years • ≥ 50 to < 60 years • ≥ 60 years 	Informed consent	Categorical descriptives
Sex, race, and ethnicity	
 • eCRF categories • Race group 
 ○ White ○ Non-white 	Screening Period	Categorical descriptives

